## STATEMENT OF COMPLIANCE

The trial will be conducted in accordance with International Council on Harmonisation Good Clinical Practice (ICH GCP), applicable United States (US) Code of Federal Regulations (CFR). The Principal Investigator will assure that no deviation from, or changes to the protocol will take place without prior agreement and documented approval from the Institutional Review Board (IRB), and the Investigational New Drug (IND) or Investigational Device Exemption (IDE) sponsor, if applicable, except where necessary to eliminate an immediate hazard(s) to the trial participants. All personnel involved in the conduct of this study have completed Human Subjects Protection and ICH GCP Training.

The protocol, informed consent form(s), recruitment materials, and all participant materials will be submitted to the IRB for review and approval. Approval of both the protocol and the consent form(s) must be obtained before any participant is consented. Any amendment to the protocol will require review and approval by the IRB before the changes are implemented to the study. All changes to the consent form(s) will be IRB approved; a determination will be made regarding whether a new consent needs to be obtained from participants who provided consent, using a previously approved consent form.

## 1 PROTOCOL SUMMARY

### 1.1 SYNOPSIS

Title:	Transabdominal plane (TAP) Blocks for Laparoscopic Inguinal Hernia Repair
Grant Number:	
Study Description:	Inguinal hernias are bulges in the groin region that arise from weaknesses in the abdominal wall. Often, due to discomfort, pain or cosmetic dissatisfaction, these hernias must be surgically repaired. The use of a transabdominal plane (TAP) block—a local injection given in the abdomen to block pain receptors on nerves—during surgery can presumably decrease postoperative pain. The aim of our study is to investigate whether the use of a TAP block can decrease the use of opioids and pain scores after surgery.
Objectives*:	The aim of our study is to examine outcomes and pain control after surgery in patients who underwent laparoscopic inguinal hernia repair (IHR) with the use of perioperative transabdominal plane (TAP) block. Research Question: Does transabdominal plane block improve pain when undergoing inguinal hernia repair?
Endpoints*:	To evaluate whether preoperative TAP blocks improve pain score (primary end point) and decrease opioid use (secondary endpoint) after an inguinal hernia repair. Other end points- complications after surgery.
Study Population:	We will be enrolling 100 patients from Mount Sinai Hospital undergoing laparoscopic inguinal hernia repair.
Phase* or Stage:	
Description of Sites/Facilities Enrolling Participants:	All enrollment will occur at one site (Mount Sinai Hospital) at Faculty Practice Associates and Emergency Department.
Description of Study Intervention/Experimental Manipulation:	The study intervention is the administration of a TAP Block (0.25% bupivacaine or placebo (Saline). For patients weighing <100 kg, they will receive a total of 50 mL (25 mL on each side of the abdominal wall). If patients weigh >100 kg, they will receive a total of 60 mL (30mL on each side of the abdominal wall). The TAP plane is identified using ultrasound. All anesthesiologists working with the surgical attendings involved in this study have been trained in this technique; it is a routine part of their practice. Anesthesiologists will be performing the block.
Study Duration*:	2 Years
Participant Duration:	2 Weeks

### 1.2 SCHEMA

### 1.3 SCHEDULE OF ACTIVITIES

## 2 INTRODUCTION

## 2.1 STUDY RATIONALE

Pain after surgery is common among patients. This pain may contribute to using of opioids and other medications to control discomfort and pain. Other clinical trial studies for hernias have shown potential benefit of a perioperative block on pain post-surgery. This investigation of using the TAP block peri-operatively will provide important information on pain control for the laparoscopic inguinal hernia repair.

## 2.2 BACKGROUND

Inguinal hernias are bulges in the groin region that arise from weaknesses in the abdominal wall. Often, due to discomfort, pain or cosmetic dissatisfaction, these hernias must be surgically repaired. The use of a transabdominal plane (TAP) block—a local injection of bupivacaine given in the abdomen to block pain receptors on nerves—during surgery can presumably decrease postoperative pain. Currently, TAP blocks are approved for use and performed based on surgeon preference (e.g. some surgeons perform them on every case, others variably, etc.). The aim of our study is to investigate whether the use of a TAP block can decrease the use of opioids and pain scores after surgery.

Papers - PMID: 27555193, 29605459, 25558340, 23060979 - have analyzed their data using chi-square test/ Fisher exact test and Student t-test/Wilcoxon Signed rank test. This method of analysis does not take into account longitudinal nature of the data. We will take into account the fact that same patient is being examined throughout the study at different time points. In addition to the above mentioned statistical procedures we will examine the trajectory between the TAP group vs. placebo group over time using mixed effects models (will also take into account correlation structure between different time points) for the outcome of opiate consumption and pain scores.

## 2.3 RISK/BENEFIT ASSESSMENT

### 2.3.1 KNOWN POTENTIAL RISKS

There always exists the potential for loss of private information. There is also always the risk that the TAP block may not provide adequate analgesia.

There is also a risk of bowel perforation during TAP injection. However, this risk is minimal given that the bowel is well visualized with ultrasound guidance and thus avoided at all costs.

All injections of anesthetic carry a <1% risk of local anesthetic systemic toxicity (LAST) which can cause seizures or even cardiac arrest.

As all risks for harm are those included as part of standard treatments, there are no provisions for harm or injury. Any follow-up tests, treatments, or procedures will be performed at cost to the participant.

### 2.3.2 KNOWN POTENTIAL BENEFITS

It is possible that the patient may receive no benefit from this study. However, benefits may include improved postoperative pain management, decreased opioid use and quicker return to normal function and daily activities.

The larger population will benefit from the increased knowledge of TAP use for hernia repair, allowing future patients with inguinal hernia to be more knowledgeable about the benefits and risks of this option.

### 2.3.3 ASSESSMENT OF POTENTIAL RISKS AND BENEFITS

All physical risks for harm are those included as part of standard treatments, there are no added provisions for harm or injury due to the study. All information will be stored securely and in accordance with IRB policies and expectations. This treatment could prove beneficial to the patient and the larger public in terms of pain control and reducing opioid use.

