## 6 STUDY INTERVENTION(S) OR EXPERIMENTAL MANIPULATION(S)

### 6.1 STUDY INTERVENTION(S) OR EXPERIMENTAL MANIPULATION(S) ADMINISTRATION

#### 6.1.1 STUDY INTERVENTION OR EXPERIMENTAL MANIPULATION DESCRIPTION

The study intervention is 0.25% bupivacaine. This neural block will be administered at the transabdominal plane. Other clinical trials have shown benefit of a neural block for hernia repairs on pain scores. We believe this intervention will work according to similar mechanism.

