### 8.2 SAFETY ASSESSMENTS

As all procedures are according to standard of care, all parts of care will be administered and any complications and events will be tracked.

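### The standard-care risk statements do not cover the saline TAP injection, and two definitions of the study intervention leave it unclear whether harm from that injection must be reported

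*Combined protocol and SAP*

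**What the plan says.** On risk, Section 2.3.3 states: "All physical risks for harm are those included as part of standard treatments". Section 2.3.1 says the same and draws a consequence: "As all risks for harm are those included as part of standard treatments, there are no provisions for harm or injury". It then adds: "Any follow-up tests, treatments, or procedures will be performed at cost to the participant". Section 8.2 opens its safety plan with "As all procedures are according to standard of care". Sections 8.3.1 and 8.3.2 expect no adverse events, on the ground that the intervention is a standard-of-care analgesic drug.

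On what is injected, Sections 4.1 and 6.1.2 randomize patients to bupivacaine or normal saline, given on both sides of the abdominal wall. Section 2.3.1 lists a risk of the injection itself: "There is also a risk of bowel perforation during TAP injection".

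On what counts as the study intervention, the synopsis (Section 1.1) reads: "The study intervention is the administration of a TAP Block (0.25% bupivacaine or placebo (Saline". Section 6.1.1 reads: "The study intervention is 0.25% bupivacaine". Section 8.3.1 defines an adverse event as one resulting from the study intervention, and Sections 8.3.5 and 8.3.6 send to the IRB those events and serious events that are due to it.

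**The concern.** The saline injection exists only because the trial needs a blinded control. A blanket statement that every physical risk belongs to standard treatment leaves out the one procedure that is purely research, and the reason given for expecting no adverse events describes a drug that half the patients do not receive. The statement that there are no provisions for injury is derived explicitly from this premise, so it loses its stated basis for those patients.

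The reporting rule is also insecure. If an injection injury occurred in the saline arm, a reader of the synopsis would report it, while a reader of Section 6.1.1 could conclude that the rule does not apply. What is at stake is participant protection and a clear reporting duty. The efficacy analysis is not affected.

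**Working it through.** The plan gives no figure on this point, so there is none to reproduce. The check is mainly a comparison of sections.

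**Step 1: what usual care is.** Section 2.2 describes the block as an injection of bupivacaine and says "TAP blocks are approved for use and performed based on surgeon preference". Usual care, as documented, is therefore either a bupivacaine block or no block. Saline appears only as the placebo (synopsis, Sections 4.1, 6.1.2 and 6.3). No section describes a saline TAP injection as usual care.

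**Step 2: which listed risks apply to saline.** Section 2.3.1 ties bowel perforation to the TAP injection and systemic toxicity to injection of anesthetic. A saline patient carries the first risk and not the second.

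**Step 3: how many patients.**
- Inputs: 100 patients (synopsis, Section 5.5), 1:1 allocation (Section 6.3), two sides per patient (Section 6.1.2).
- Patients given saline: 100 × 1/2 = 50.
- Saline injections: 50 × 2 = 100. This counts injections given, not needle exposures added by the trial.
- Patients with needle exposure added by the trial: let p be the share who would have had a bilateral block in usual practice. Every trial patient receives the injection, so the number is 100 × (1 − p). At p = 1 it is 0; at p = 0 it is 100. The documents do not give p.

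**Step 4: what the reporting rule covers.** Take a needle injury and apply the trigger in Sections 8.3.1, 8.3.5 and 8.3.6 under each available reading.

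| Reading of study intervention | Bupivacaine arm | Saline arm |
|---|---|---|
| Synopsis: block with either solution | Covered | Covered |
| Section 6.1.1 as the bupivacaine block procedure (its second sentence speaks of the block being administered) | Covered | Doubtful |
| Section 6.1.1 strictly as the drug | Doubtful, since the needle and not the drug did the harm | Doubtful |

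The three readings give three different answers, and no section says which governs. Usage elsewhere does not settle it. Sections 5.4, 6.3 and 9.4.9 name placebo separately from the intervention, while Sections 4.4, 6.4, 7.1 and 8.1 use intervention for what every patient receives.

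**Step 5: whether another rule closes the gap.** Section 8.2 tracks complications and events without limiting them by arm, but it does not send them to the IRB. Section 8.3.3.3 refers to study procedures, but only to judge whether an adverse event is expected. Definition and reporting of unanticipated problems are marked not applicable (Sections 8.4.1 to 8.4.3), as are safety analyses (Section 9.4.4). Oversight rests with the research team and investigators (Section 10.1.6). The adverse-event rule is therefore the main stated route by which an injection injury would reach the IRB.

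**The case against.** The strongest reply is that this is loose wording and excludes nothing. The synopsis expressly includes saline, Section 6.1.2 covers both solutions under one administration heading, and several sections call whatever was injected the intervention. On that footing saline harm is already reportable. This stands to the extent that a reader might infer from Section 6.1.1 that saline-injection harm falls outside the adverse-event rules. That inference takes one of two conflicting definitions as controlling, and the documents do not support it as fact. What they support is that the duty is unclear.

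Three further inferences are tempting and should not be drawn:
- *That the complication comparison is biased against the block.* Section 8.2 tracks complications in all patients and Section 9.4.9 compares them between arms. Nothing says that the comparison is built from IRB reports.
- *That the IRB is unaware of the risk.* Under the Statement of Compliance it reviews and approves the protocol, which discloses both the saline arm and the perforation risk.
- *That participants are told no risk is added.* The consent form is not in the text available for review, and Section 10.1.1.1 says it describes procedures and risks in detail.

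It can also be said that blinded classifiers could not apply a rule that differs by arm. That is correct if they are blinded. However, Section 4.1 has the envelope alert the anesthesiologist or surgeon to the allocation, while Sections 8.3.2 and 8.3.3.2 give classification to the attendings and the principal investigator. Even with full blinding, the rule would still not say whether needle harm counts.

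Finally, Section 2.3.1 calls the perforation risk minimal. That bears on how often the problem would arise. It does not make the statement accurate for the saline arm.

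**Conclusion.** The concern holds in two parts. First, the standard-care statements in Sections 2.3.1, 2.3.3 and 8.2, and the expectation of no adverse events in Sections 8.3.1 and 8.3.2, are wrong as written for the roughly 50 of 100 patients assigned to saline. Second, the synopsis and Section 6.1.1 define the study intervention differently, and because adverse-event definition and reporting depend on that term, it is unclear whether harm from the saline injection must go to the IRB.

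The figure of 50 assumes full enrolment and exact 1:1 allocation. It counts patients whom the risk statement does not describe and is not an estimate of added harm. The number of patients with added needle exposure depends on usual surgeon practice, which is not quantified, and no perforation rate is given, so no expected number of injuries can be derived. This should be corrected as a matter of participant protection. It does not call the primary comparison into question.

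**What to change.** Make one amendment:

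1. In Section 6.1.1, define the study intervention as the TAP injection of either solution, in line with the synopsis, and use the term in that sense throughout.
2. State that Sections 8.3.1 to 8.3.6 apply identically to both arms.
3. Correct Sections 2.3.1, 2.3.3, 8.2, 8.3.1 and 8.3.2 to say that the saline injection is a research procedure with needle risk, and drop the reasoning that relies on a standard-of-care drug.
4. Check that the consent text agrees.
5. Have the statements on injury provisions and participant cost in Section 2.3.1, and the related sentence in Section 2.3.3, reconciled with the corrected risk statement. How they are resolved is for the sponsor and the IRB.

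The cost is protocol wording and, if needed, consent wording, with IRB review. The downside is a less favourable risk statement and possibly a few more reportable events. Sample size, data collection and analysis do not change.

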## 3 OBJECTIVES AND ENDPOINTS

OBJECTIVES	ENDPOINTS	JUSTIFICATION FOR ENDPOINTS	PUTATIVE MECHANISMS OF ACTION
Primary			
Do TAP blocks improve pain score?	Change in pain score for the intervention versus placebo groups.	Assessing causal effect of TAP block on pain levels through the RCT design is the gold standard approach.	
Secondary			
Do TAP blocks decrease opioid and other pain medication use after surgery?	Assessing number/volume of pain medication.	TAP blocks should directly impact pain medications usage.	
Tertiary/Exploratory			
Does TAP block usage affect complications after surgery?	Assessing complication rate differences between the intervention and placebo groups with regards to complications.	Complications can differ based on treatment. We want to assess if complications rates differ between the two groups.	

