## 4 STUDY DESIGN

### 4.1 OVERALL DESIGN

After receiving approval for the study, we will conduct a prospective single institution randomized clinical trial assessing if using a TAP block perioperatively can reduce pain scores after surgery. Other endpoints include whether there are differences in pain medication usage and complications.

Patients will be screened by research team members and attending surgeons. If the patient is interested, we will consent them for the study after they understand the study details, procedures, and expectations. We will then consent using IRB approved study consent forms and procedures. Patients will undergo a laparoscopic inguinal hernia repair according to standard procedures. Our study will assess if a TAP block impacts pain scores. Patients will be randomized to receive the intervention or placebo. Sequentially numbered sealed opaque envelopes with group allocation inside will alert the anesthesiologist/ surgeon to order Tap block composed of 0.25% bupivacaine or placebo (normal saline).

Inguinal hernia repair will be performed in standard fashion that each individual surgeon is familiar with. No additional tests or blood work outside the standard of care for IHR will be performed for research purposes. In addition, some patients will be given TAP blocks before surgery to help in pain management. In addition, patients will be discharged with a worksheet on which they are to record analgesic use and pain scores on postoperative days one, two, three and four. They are expected to bring the completed log to their two-week follow up visit with their surgeon. Patients may also expect to receive a phone call from a member of the surgical team to remind them to record these metrics.

The TAP block is done pre-procedure using 0.25% bupivacaine. If patients weigh<100 kg, they will receive a total of 50 mL (25 mL on each side of the abdominal wall). If patients weigh>100 kg, they will receive a total of 60 mL (30mL on each side of the abdominal wall). The TAP plane is identified using ultrasound. All anesthesiologists (not surgeons) working with the attendings involved in this study have been trained in this technique; it is a routine part of their practice. It is anesthesiologists who will be performing the block.

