## 9 STATISTICAL CONSIDERATIONS

### 9.1 STATISTICAL HYPOTHESES

- Primary Endpoint(s):

We hypothesize that patients randomized to the intervention will have lower pain scores as compared to the placebo arm.

- Secondary Endpoint(s):

We hypothesize that patients randomized to the intervention will have lower intake of opioid and as compared to the placebo arm.

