#### 9.4.3 ANALYSIS OF THE SECONDARY ENDPOINT(S)

The secondary endpoint will be assessed using either Chi-square, Fisher's exact, Mann Whitney U or the best test for the data.

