#### 9.4.5 BASELINE DESCRIPTIVE STATISTICS

Demographic and pre-intervention variables will be described as following:

Categorical variables will be described using the frequency and proportions. Continuous variables will be described using median and the interquartile range (Q1, Q3). Chi-square or Fisher's test and Student's t-test or Mann-Whitney U test will be used depending on type of data.

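### The secondary endpoint is opioid use in the synopsis but a number or volume of all pain medication in section 3, with no common unit, no split by drug class and no single named test

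*Combined protocol and SAP*

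**What the plan says.** **Drug scope.** The synopsis (1.1) sets out to evaluate whether the block will "decrease opioid use (secondary endpoint) after an inguinal hernia repair". Section 3 asks "Do TAP blocks decrease opioid and other pain medication use after surgery". Section 4.1 is wide as well: "Other endpoints include whether there are differences in pain medication usage and complications". Section 9.1 states the hypothesis as "lower intake of opioid and as compared to the placebo arm". That sentence names opioids but seems to have lost words after the conjunction, so it does not settle the scope. Section 2.2 speaks of opiate consumption.

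**Measure.** Section 3 gives "Assessing number/volume of pain medication" and nothing more. No section states a common unit, an equivalence conversion, a per-patient summary (daily or cumulative) or a rule separating opioids from other drugs. Section 6.5 leaves analgesic use unrestricted and has patients record both opioid and over-the-counter drugs. Section 4.1 has them do so on postoperative days one to four.

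**Test.** Section 9.4.3 lists chi-square and Fisher's exact, then "Mann Whitney U or the best test for the data". Section 2.2 also promises a mixed model over time: "In addition to the above mentioned statistical procedures we will examine the trajectory". Section 9.4.3 does not mention it.

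**The concern.** Lower opioid use is part of the trial's stated aim (1.1, 2.2) and one of its expected benefits (2.3.2). From these sections an analyst cannot tell whether over-the-counter tablets belong in the secondary endpoint, or in what unit intake is to be added up.

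If section 3 is applied as a single count, two errors become possible. Patients who replace opioid tablets with over-the-counter tablets leave the count unchanged, so a real opioid effect is hidden. A fall in over-the-counter use alone lowers the count and can be reported as if opioid use had fallen. Restricting the count to opioids cures both errors, but one strong tablet still counts the same as one weak tablet.

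The test list is a smaller matter. Chi-square and Fisher's exact need a categorical variable, such as any opioid use, that no section defines. All the descriptions of the endpoint are of an amount.

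**Working it through.** The plan gives no effect size, variance, usage rate or power for this endpoint, so it has no figure of its own to reproduce. The check sets out the mechanism and then its possible size under stated assumptions.

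**Inputs from the documents.** 100 patients allocated 1:1 (9.2), so 50 per arm; two-sided 0.05 (9.4.1); Mann-Whitney as one of the listed tests (9.4.3).

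**Assumed, not from the documents.** Opioid tablets per patient follow a zero-inflated negative binomial with dispersion 1.5. The settings for extra zeros and the mean of the count part are 30% and 6, 50% and 6, or 20% and 8. Over-the-counter tablets are negative binomial with dispersion 1.5 and mean 4, 8 or 12, independent of opioid use. This makes nine settings.

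**Mechanism.** Let o and c be the mean opioid and over-the-counter counts, f the proportional fall in opioids, and r the share of avoided opioid tablets replaced one for one. The proportional fall in the pooled count is o × f × (1 − r) / (o + c). Take 30% zeros and count mean 6, so o = 0.7 × 6 = 4.2, with c = 8 and f = 0.5:
- r = 0: 2.1 / 12.2 = 17%
- r = 0.5: 1.05 / 12.2 = 9%
- r = 1: 0%
- opioids unchanged, over-the-counter halved: 4 / 12.2 = 33%
- opioids halved and over-the-counter down 25%: (2.1 + 2) / 12.2 = 34%

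**Simulated power** (significant in the favourable direction; range over the settings):

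| Scenario | Opioid-only total | One pooled count |
|---|---|---|
| Opioids −50%, none replaced | 19-61% | 10-50% |
| Opioids −50%, half replaced | 19-61% | 5-13% |
| Opioids −50%, all replaced | 19-61% | 1-4% |
| Opioids unchanged, over-the-counter −50% | 2-3% | 29-83% |
| Opioids −50%, over-the-counter −25% | 19-61% | 52-82% |
| Both −50% | 19-61% | 90-99% |

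The 25% row used 4,000 trials per cell and the others 6,000, so the Monte Carlo standard error is at most √(0.25/4,000) = 0.8 points. The first four rows show masking and imitation. The last two show pooling ahead.

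**Unit.** This compares an opioid total in a common unit with an opioid tablet count, for a 50% fall. If patients need a given amount and half receive tablets two or three times as strong, the common unit gains 2-13 points of power (for example 63 v 56% and 61 v 48% in the third opioid setting). If strength (ratio 2) is unrelated to number, it costs 1-6 points (for example 54-56 v 59-61%). Power does not decide the unit; interpretation does.

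**Test choice, no true difference.** Choosing a test blind to arm gives a type I error of 4.8-4.9%. Taking the smaller p-value of Mann-Whitney and Fisher on any use gives 5.5-6.5%. Adding uncorrected chi-square gives 6.9-8.0%.

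**The case against.** **No section says the drugs will be summed.** This stands. Sections 1.1, 2.2 and 9.1 name opioid or opiate intake and 6.5 collects both classes, so a reasonable reading is that the two are analysed side by side. Volume may also mean amount taken. A reader might infer that the plan commits to one pooled tablet count. It does not, and the masking figures apply only if section 3 is carried out that way. What remains is that the text permits it and specifies nothing else.

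**Pooling can be the stronger test.** This also stands. Section 3 expects the block to affect analgesic use generally. If over-the-counter use falls by even half as much as opioid use, the pooled count wins in all nine settings (52-82% v 19-61%). It wins in seven of nine when use of the two classes is strongly correlated. But it then supports a statement about all analgesics, not about opioids.

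**The test list is a choice by data type.** Section 9.4.5 does the same for baseline tables: "will be used depending on type of data". Section 6.3 keeps the analyst unaware of individual treatment. A reader might infer that the open list inflates the false-positive rate. That would require picking by p-value, which no section proposes. The mixed model in 2.2 is described as additional, so it is not a rival analysis. What stands is only that no single test is named.

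**The worksheet is not in the documents.** It may already capture drug, strength and number. If so, the fix is easier, but the endpoint still needs its definition.

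**Conclusion.** The point holds as a defect of endpoint definition. The sections disagree on drug scope, and the section 3 measure, as written, has no unit or class split that would let it show whether opioid intake fell. This is worth correcting before unblinding but is not critical: it touches a secondary endpoint, and the primary pain-score test in 9.4.2 is unaffected.

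The size is conditional. If all drugs are counted together, the chance of detecting a halving of opioid intake ranges from 1-4% (full replacement) to 90-99% (over-the-counter use also halves), against 19-61% for an opioid-only total throughout. With opioid intake unchanged, halved over-the-counter use would give a significant pooled result in 29-83% of trials. Every percentage rests on assumed distributions and is not a forecast for this trial. That pooling can hide or imitate an opioid effect does not depend on those distributions. The case for change is that the endpoint should answer the opioid question, not that it gains power. The unnamed test is a minor addition.

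**What to change.** - Reconcile the drug scope in 1.1, 3, 4.1 and 9.1, and complete the 9.1 sentence.
- Define the secondary endpoint as each patient's total opioid intake over the recorded worksheet days 1-4, in oral morphine equivalents, zero if none was taken. Fix the conversion table before unblinding.
- Fix a rule for missing worksheet days before unblinding as well, because 4.4 accepts a partly completed worksheet.
- In 9.4.3, name one two-sided Wilcoxon rank sum test at 0.05 and delete the open-ended option.
- Report non-opioid pain medication separately, as a supportive measure with no claim of success of its own, or test it only after the opioid endpoint. Two independent tests at 0.05 with either counting as success would give 1 − 0.95² = 9.75%.
- List any opioid use (yes/no) and the 2.2 mixed model as supportive in 9.4.3.
- Check that the worksheet asks for drug name, strength and number per day.

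**Cost.** The fix takes some wording, a worksheet check and one conversion step; no visit, treatment or sample-size change is needed. The downsides are reliance on a conversion table, a possible loss of 1-6 points of power against a tablet count, and dependence on what the worksheet captures. Day-of-surgery use is also left out unless the trial records it elsewhere.
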